11.1.4.2. Blood Loss

As defined in Section 10.3.3.2.1, the measure of blood loss per patient will be computed using two different methods:

Method 1: treating the whole eschar removal process as one continuous procedure

 Method 2: summing the blood loss computed per procedure over all procedures carried out to remove eschar

Descriptive statistics of the blood loss values will be provided by treatment group.

The imputation of missing values, involving the multiple imputations procedure, and further statistical analysis are detailed in Section 10.1.3.2. An overall estimate of the treatment difference with its standard error will be reported, together with the final combined p-value.

The analysis with less missing values will be regarded as more reliable and is therefore considered the main analysis. The other analysis is considered supportive.

As sensitivity analysis, the analysis outlined above will be repeated using the PP instead of the FAS as analysis population.

A supportive analysis will be performed adjusting for other baseline variables that are imbalanced, based on the analyses described in Section 11.1.1.

Note: No wound level analysis of this endpoint is possible, since blood loss cannot be attributed to single target wounds.

11.1.4.3. Area of Autograft in DPT Wounds

For the purpose of the main analysis, the mean percent area of autograft in DPT wounds will be compared on a subject level between NexoBrid and SoC. This analysis will be restricted to subjects having at least one DPT target wound. Descriptive statistics of the observed values on a subject level (including the number of missing values) will be provided by treatment group. The imputation of missing values, involving the multiple imputations procedure, and further statistical analysis are detailed in Section 10.1.3.3. An overall estimate of the treatment difference with its standard error will be reported, together with the final combined p-value.

As sensitivity analysis, the main analysis outlined above will be repeated using the PP instead of the FAS as analysis population, also restricted to subjects having at least one DPT target wound.

Supportive analyses on a subject level will include adjustments for additional baseline variables which are found to be imbalanced, based on the analyses described in Section 11.1.1.

As an additional analysis, the percent area autografted in DPT target wounds will be analyzed on a target wound level. This analysis will be restricted to DPT target wounds only. Descriptive statistics will be provided on a target wound level for each treatment group. The differences in the distribution of percent area autografted in DPT wounds between the treatment groups will be tested using a mixed linear regression model with patient as the random effect that accounts for within-subject correlation between target wounds.

11.1.4.4. Incidence of Autograft in DPT Wounds

This is a binary yes/no variable and the proportion of Deep Partial Thickness TWs that were autografted will be compared (on a wound level). Missing data for the main analysis and for the two sensitivity analyses will be handled by the methods described in Section 10.1.3.4. The comparison of NexoBrid versus SoC will be conducted using logistic regression within the generalized estimating equations (GEE) framework that accounts for within-subject correlation between target wounds. The explanatory variables in the model will include treatment, center, age, %TBSA (wound level), proportion of the FT area of a patient and number of TWs (1,2,3-4, \geq 5). The odds ratio of requiring Autograft for NexoBrid versus SoC will be estimated from the model, as well as 95% confidence intervals and the level of statistical significance.

As sensitivity analysis, the procedure outlined above will be repeated using the PP instead of the FAS as analysis population.

Supportive analyses will include adjustments for baseline variables which are found to be imbalanced, based on the analyses described in Section 11.1.1.

These analyses will only take into account DPT target wounds.

11.1.5. Safety Analyses

All safety variables except for the first safety endpoint "time to reach complete wound closure", which will be evaluated using the FAS, will be evaluated on the safety set.

11.1.5.1. Time to Reach Complete Wound Closure

For the purpose of the main analysis, time to reach complete wound closure will be compared between the NexoBrid and SoC at a wound level using a method of survival analysis with clustered data that is based on appropriate assumptions. By "clustered data", we refer to the

multiple target wounds that can occur in a patient. As stated in the protocol, a non-inferiority margin will be incorporated into the analysis that will represent a 7-day advantage to the SoC group. This will be done by adding 7 days to the wound closure times in the SoC group. After that, the proportional hazards assumption will be checked in the same way as in the analysis of the timely eschar removal endpoint. I.e. a Cox regression model will be fitted with covariates treatment, center, age, %TBSA, proportion of the FT area of a patient, number of TWs (1,2,3-4, ≥5) and a variable representing the interaction between time since randomization and treatment group. The latter coefficient will be tested to be nonzero. Additionally, a log likelihood test comparing the model fit of a model with all time by covariate interactions added with a model without these interactions will be computed. The proportionality assumption will be rejected if one of these tests yields a significant result at the 10% level. If the proportional hazards assumption is appropriate we will use a marginal Cox regression analysis with a robust sandwich estimator. If not, then we will use a parametric frailty model. Either method can be implemented in SAS (see Gharibvand and Liu, 2009 for details). The marginal Cox regression model is implemented in the PHREG procedure and the robust variance option is implemented by specifying the COVS(AGGREGATE) option. This induces the use of the robust variance method of Binder et. al. [22]. The parametric frailty model will be implemented using the following SAS-code:

```
PROC PHREG DATA=burn_data;
CLASS Subject_id treatment_group centergroup numtw;
MODEL time*status(0) = treatment_group centergroup age tbsa pctFT numtw;
RANDOM Subject_id;
HAZARDRATIO "Frailty Model" treatment_group;
RUN;
```

where subject_ID is a unique identification number for each patient, time is the time to wound closure on a wound level, status is an indicator whether the wound has achieved complete wound closure or not (censoring indicator), treatment_group gives the treatment group, centergroup is the stratification factor defined in Section 11.1.11, age is the patient's age, tbsa is the overall percent TBSA of a patient, pctFT is the proportion of the FT area of a patient, numtw is the number of TWs (1,2,3-4, ≥5) of the patient and burn_data is a SAS data set containing the required information. These methods include information on all the target wounds of each patient and account for any within-patient correlation. Missing information due to incomplete follow-up is incorporated naturally into such analyses as censored observations.

In case the proportional hazards assumption is rejected and the parametric frailty model is used, the underlying proportional hazards assumption (conditional on the frailty term) will be checked by adding a variable representing the interaction between time since randomization and treatment group to the model. In case the coefficient of the latter term is significantly different from zero (at the 5% level) a further sensitivity analysis using an accelerated failure time (AFT) model with shared frailty will be performed. This model will be implemented using the following SAS-code:

```
PROC NLMIXED DATA=burn_data;
BOUNDS gamma>0;
linp = b0 + b1*treatment_group + b2*age1 + b3*age2 + b4*age3 + b5*tbsa1 +
b6*ft1+ b7*number_tw2+ b8*number_tw3 + b9*number_tw4 + b10*US + b11*EEU +
b12*WEU + z;
alpha = exp(-linp);
G_t = 1/(1+alpha*time**gamma);
g = alpha*gamma*time**(gamma-1)/(1+alpha*time**gamma)**2;
l1 = (censor=0)*log(g) + (censor=1)*log(G_t);
model time~general(l1);
RANDOM z ~ normal(0, sigma) subject=subject_id;
RUN;
```

where subject_ID is a unique identification number for each patient, time is the time to wound closure on a wound level. Censor is a censoring indicator, treatment_group gives the treatment group, age1-age3 are indicator variables for a subject being in age group A1 − A3 respectively (per age groups defined in Section 11.1.11), ft1is an indicator for a subject with proportion of the FT area <20% out of the total burned area (group C1, defined in Section 11.1.11), TBSA1 is an indicator for a subject with overall %TBSA in (1% to 15%), inclusive (group B1, defined in Section 11.1.11), number_tw2 is an indicator variable for the subject having 2 target wounds (patient level), number_tw3 is an indicator variable for the subject having 3-4 target wounds (patient level), number_tw4 is an indicator variable for the subject having ≥5 target wounds (patient level), US, EEU and WEU are indicator variables for the individual being in region US, EEU and WEU (patient level) and burn_data is a SAS data set containing the required information.

Kaplan-Meier curves will be presented graphically to display the distribution of time to complete wound closure under the two treatments.

If any of the baseline factors are found to be significantly different between the treatment groups (based on the analyses described in Section 11.1.1), then the factor will be included as an extra adjusting covariate in a supportive analysis of time to complete wound closure.

As an additional analysis, the time to complete wound closure will be analyzed on a subject level. Kaplan-Meier curves will be presented graphically to display the distribution of time to complete eschar removal under the two treatments on a subject level. Median time to complete eschar removal will be estimated for each treatment group with a 95% confidence interval. Furthermore, descriptive statistics for time to complete eschar removal will be presented. The treatment groups will be compared using either a Cox regression model (if the proportional hazards assumption appears to hold), or a generalized Wilcoxon-Gehan test (if the proportional hazards assumption does not hold), as described in Section 11.1.3 for the main analysis of the primary efficacy endpoint.

As supportive analyses, the time to reach 100% wound closure will be analyzed on a wound level (similar to the main analysis outlined above) and on a subject level (similar to the additional analysis outlined above).

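### The proportional-hazards check that selects the wound-level model makes no allowance for wounds clustered in a child, so its stated 10% level does not hold

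*SAP*

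**What the plan says.** The main wound-closure comparison in SAP 11.1.5.1 is made "at a wound level using a method of survival analysis with clustered data that is based on appropriate assumptions". The non-inferiority margin is built in first: "This will be done by adding 7 days to the wound closure times in the SoC group". Only then comes the model-selection step: "the proportional hazards assumption will be checked in the same way as in the analysis of the timely eschar removal endpoint". The main eschar-removal analysis in 11.1.3, where this check comes from, has one record per patient.

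The check has two parts, both based on a Cox model with treatment, center, age, %TBSA, FT proportion and number of target wounds. For the treatment-by-time term: "The latter coefficient will be tested to be nonzero". The second part is "a log likelihood test comparing the model fit of a model with all time by covariate interactions added with a model without these interactions". The decision rule is: "The proportionality assumption will be rejected if one of these tests yields a significant result at the 10% level".

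After a pass: "If the proportional hazards assumption is appropriate we will use a marginal Cox regression analysis with a robust sandwich estimator". The patient-aggregated variance option, COVS(AGGREGATE), is named at that point. After a fail: "If not, then we will use a parametric frailty model". For neither test does the SAP name a variance or likelihood that allows for clustering.

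The additional wound-level eschar analysis in 11.1.3 uses the same check and the same two branches, without the 7-day shift.

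**The concern.** An ordinary Cox log likelihood adds up contributions as if each wound were an independent unit. If wounds in the same child tend to close early or late together, twice the log-likelihood difference no longer follows the chi-square distribution that gives the 10% its meaning. Covariates that are constant within a child are the worst case, and every covariate in the wound-closure model is of that kind (the SAP defines tbsa, for example, as the patient's overall value). The check was legitimate for one record per patient and was carried over to several records per patient unchanged.

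At stake is which model is the main one. The marginal Cox model gives a population-average hazard ratio. The frailty model gives a hazard ratio conditional on the child. A rejection would be read as evidence of non-proportional hazards when it may partly reflect correlation. Nor does the switch cure non-proportionality: 11.1.5.1 accepts that the frailty model still assumes proportional hazards given the frailty, and a failure there only adds an accelerated failure time sensitivity analysis.

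**Working it through.** **The plan's own figures.** The SAP does not calculate how often the check would reject; 10% is a threshold. The only calculated figures for this endpoint are the sample sizes in 13.3, from D = 4(z_α + z_β)²/(ln λ)² and n = 2D/(p₁ + p₂). With unrounded quantiles the numerator is 4 × (1.960 + 1.2816)² = 42.03.
- Log HR 0.18: 42.03/0.0324 = 1297.2, rounded up to 1298; 2 × 1298/(0.64 + 0.56) = 2163.3 (stated 2164).
- HR 3.90: 42.03/1.361² = 22.7, rounded up to 23; 2 × 23/(0.62 + 0.73) = 34.1 (stated 34).

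Both reproduce. They do not bear on the check.

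**Inputs from the documents.** 145 patients (13.3). The global test has about 10 degrees of freedom: treatment 1, region 3 (four regions, 11.1.8), age 1, %TBSA 1, FT proportion 1, number of target wounds 3. Two tests at 10% would, if independent, give 1 − 0.9² = 19% for the either-of-two rule.

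**Assumed inputs.** Mean wounds per child 1.0 to 2.5; latent within-child correlation 0 to 0.7; Weibull closure times; 96% of wounds closed, with one setting at 67% because the earlier trials had 56% to 73%. The SAP does not say how time enters the interaction, so both log time and linear time were run.

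**Simulation.** 1000 trials per setting, marginal proportional hazards exactly true, no treatment effect, no 7-day shift. Monte Carlo standard error is 0.9 to 1.6 points. Rejection at 10%, in percent, log time / linear time, ordinary tests:

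| Wounds per child | Correlation | Likelihood-ratio | Treatment × time | Either test |
|---|---|---|---|---|
| 1.0 | 0 | 13.6 / 18.5 | 9.2 / 11.4 | 18.4 / 24.7 |
| 2.0 | 0 | 13.1 / 19.0 | 8.8 / 10.4 | 19.2 / 25.4 |
| 1.2 | 0.5 | 23.9 / 27.0 | 10.8 / 13.7 | 29.4 / 34.7 |
| 1.5 | 0.3 | 20.5 / 22.6 | 12.2 / 11.9 | 27.8 / 28.3 |
| 1.5 | 0.6 | 36.3 / 36.2 | 16.4 / 15.9 | 42.5 / 42.2 |
| 2.0 | 0.3 | 24.3 / 25.5 | 12.7 / 13.5 | 31.5 / 33.0 |
| 2.0 | 0.5 | 41.3 / 40.5 | 17.0 / 15.9 | 48.0 / 45.8 |
| 2.0 (67% closed) | 0.5 | 37.7 / 32.7 | 15.3 / 14.8 | 43.8 / 38.9 |
| 2.0 | 0.7 | 62.8 / 59.5 | 23.7 / 21.4 | 68.1 / 64.2 |
| 2.5 | 0.5 | 47.3 / 42.0 | 19.1 / 18.5 | 53.3 / 48.7 |
| 2.5 | 0.7 | 70.3 / 63.7 | 26.4 / 26.9 | 74.2 / 69.0 |

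A separate run of 200 trials per setting (log time) gave likelihood-ratio rejection of 10–16% with independent wounds, 16% at 1.5 wounds and correlation 0.3, and 38% at 2 wounds and correlation 0.5.

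**Patient-clustered tests, no shift.** Treatment × time alone: 10–14% (log time) or 12–16% (linear time), whatever the clustering. Global test: 9–14% or 13–23%. Either-of-two rule: still 19–24% or 21–31%.

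**With 7 days added to SoC times.** Either-of-two rule, log / linear time:
- One wound per child, no correlation, ordinary tests: 70.6 / 46.0. The 200-trial run gave 58% rejection in this setting.
- Two wounds, no correlation, ordinary tests: 92.6 / 60.4.
- Two wounds, correlation 0.5, ordinary tests: 91.4 / 70.6. Patient-clustered tests: 84.7 / 60.2.
- Clustered treatment × time test alone in that last setting: 83.2 / 49.4.

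**The case against.** Four points on the other side have weight.

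1. The SAP does not state the variance or likelihood type, so calling the tests ordinary is an inference. It is the natural reading, because the clustered variance is attached only to the model fitted after a pass.

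2. A reader might infer that within-child correlation, not non-proportional hazards, will usually decide the main wound-closure model. The documents do not support that. The shift comes before the check, and no SoC closure can then fall before day 7, so proportional hazards is false when tested unless the arms differ in an exactly offsetting way. In the two-wound, 0.5-correlation setting, replacing ordinary by clustered tests lowers rejection only from 91.4% to 84.7%, or from 70.6% to 60.2%. This objection stands, and the fix has to deal with the shift.

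3. A reader might also infer that the check rejects far above 10% in any event because of clustering. The size rests on two inputs that the documents do not give. Part of the excess is present with independent wounds: the two-test rule, plus a roughly 10-degree-of-freedom test that is somewhat liberal at this sample size. The treatment-by-time test is much less inflated (11–27% under clustering).

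4. Harm to the non-inferiority conclusion is not shown. Both branches account for within-child correlation, and 11.1.5.1 adds a subject-level analysis with no clustering. The endpoint is a safety endpoint outside the hierarchy in 11.1.9. The main eschar-removal analysis is at patient level and is unaffected.

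None of this makes the unadjusted likelihood-ratio test valid on clustered wounds. That much of the point stands for both wound-level analyses.

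**Conclusion.** The point holds in a limited form. As written, the model-selecting check in 11.1.5.1 and in the wound-level part of 11.1.3 does not have its stated 10% level once wounds are correlated within a child. Under the assumed inputs, and before any shift, the likelihood-ratio test rejects in roughly 15–27% of trials with few multi-wound children or weak correlation, and in about 33–70% with two or more wounds per child and correlation of 0.5 to 0.7. The lowest figure comes from the smaller run.

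Clustering is one of three causes. The either-of-two rule gives 18–25% on independent wounds, and for wound closure the 7-day shift is a comparable or larger cause. It follows that adding a clustered variance and changing nothing else would not bring the rule to 10%. The shift figures also depend on the assumed Weibull closure times. Severity is low: one safety endpoint outside the testing hierarchy and one additional eschar-removal analysis.

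**What to change.** Either of two edits would do.

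**Simpler: fix the model in advance.** In 11.1.5.1, name the marginal Cox model with patient-aggregated sandwich variance as the main wound-closure model, give the frailty model as a sensitivity analysis, and report the proportional-hazards diagnostics descriptively. This removes the effects of clustering, the two-test rule and the shift on model choice together. The text should also say which hazard ratio the non-inferiority statement refers to, since 13.3 took its hazard ratios for this endpoint from shared-frailty fits.

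**If a data-driven choice is kept:**
- Replace both tests with Wald or score tests that use the patient-clustered sandwich variance (PHREG COVS(AGGREGATE)).
- Let one test, treatment-by-time, decide at one overall level, and report the covariate-by-time terms descriptively.
- State how time enters the interaction. Log time stayed closer to nominal in the simulations.
- State whether the check uses shifted or unshifted SoC times, and how a rejection caused by the shift itself is to be handled.

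The wound-level part of 11.1.3 can take the same wording without the shift. The cost is a few sentences and a variance option that the SAP already names. No new data are needed.

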MODEL time*status(0) = treatment_group centergroup age tbsa pctFT numtw;

RANDOM Subject_id;

HAZARDRATIO "Frailty Model" treatment_group;

RUN;
```

where subject_ID is a unique identification number for each patient, time is the time to complete eschar removal on a wound level, status is an indicator whether the wound has achieved complete eschar removal or not (censoring indicator, 0 for censor and 1 for complete ER event), treatment_group gives the treatment group, centergroup is the stratification factor defined in Section 11.1.11, age is the patient's age, TBSA is the overall percent TBSA of a patient, pctFT is the proportion of the FT area of a patient, numtw is the number of TWs $(1,2,3-4, \ge 5)$ of the patient and burn_data is a SAS data set containing the required information. These methods include information on all the target wounds of each patient and account for any

within-patient correlation. Missing information due to incomplete follow-up is incorporated naturally into such analyses as censored observations.

Kaplan-Meier curves will be presented graphically to display the distribution of time to complete eschar removal (on a wound level) under the two treatments.

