11.1.9. Handling of Multiple Comparisons

Unless otherwise specified, all statistical tests will be conducted against a two-sided alternative hypothesis, employing a significance level of 0.05. The primary and secondary endpoints of efficacy will be tested in a hierarchy, so as to preserve the nominal significance levels:

- 1. Primary: time to complete eschar removal
- 2. Secondary: Incidence of surgical excision
- 3. Secondary: Blood loss
- 4. Secondary: Area of Autograft in DPT wounds

5. Secondary: Incidence of Autograft in DPT wounds

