MW2010-03-02 (NexoBrid vs SoC): -9.39

Standard Error: 6.28

Anticipated difference: -9.39+6.28/2=-6.25

Using the normal approximation to the Wald test statistics (see for example Shih (1997)) we obtain that a total sample size of 1590 patients (922 evaluable) is needed to achieve a power of 90% using a two-sided significance level of 5%. This means that a sample size of 795 subjects per arm would be required to obtain the minimum number of evaluable subjects for

90% power in this endpoint.

Blood Loss

Estimate based on study MW2004-11-02

Estimated mean blood loss from study MW2004-11-02: NexoBrid 421.93 ml; SoC 1024.27 ml

Standard errors: NexoBrid 129.52; SoC 240.98

Difference: -602.33; Standard error of difference: 273.58

Anticipated difference: -602.33 + 267.75 / 2 = -468.47

Using a two-sided two-sample t-test with a two-sided significance level of 5%, the total number of evaluable patients needed to achieve a power of 90% is 346 (173 per group). Incorporating a rate of missing values of 30%, a total of 494 patients (247 per group) needs to be enrolled to achieve a power of 90%.

Estimate based on study MW2010-03-02

Note: In the MW2010-03-02 study, a different formula for the calculation of blood loss, than will be applied to the CIDS study, was used. However, both formulas try to estimate the same quantity and are therefore considered comparable.

Estimated mean blood loss from study MW2010-03-02: NexoBrid 14.17 ml; SoC 814.51 ml

Standard errors: NexoBrid 66.15; SOC 167.74

Difference: -800.34; Standard error of difference: 156.08

Anticipated difference: -800.34 + 156.08 / 2 = -722.30

Using a two-sided two-sample t-test with a two-sided significance level of 5%, the total number of evaluable patients needed to achieve a power of 90% is 56 (28 per group). Incorporating a rate of missing values of 30%, a total of 80 patients (40 per group) needs to be enrolled to achieve a power of 90%.

Time to Complete Wound Closure

In the following, a non-inferiority margin of 7 days is already implemented by adding 7 days to the wound closure times of the SoC group.

Estimate based on study MW2004-11-02

Estimated log hazard ratio from study MW2004-11-02 (NexoBrid versus SoC) = 0.49, using a Cox proportional hazards model with shared frailty adjusted for center, age, %TBSA area of the wound and number of TWs $(1,2,3-4, \ge 5)$.

Standard error = 0.63

Target log hazard ratio = 0.49 - 0.63/2 = 0.18; target hazard ratio $\lambda = 1.2$.

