The formula for total number of events D is: $D = \frac{4(z_{\alpha} + z_{\beta})^2}{(\ln \lambda)^2}$

(Piantadosi, Clinical Trials: A Methodologic Perspective, p.169)

 $z_{\alpha} = 1.96$;

 z_{β} = 1.28 for 90% power.

If the proportion of events in NexoBrid group is denoted by $p_1 = 0.64$

and the proportion of events in SoC group is denoted by $p_2 = 0.56$,

which are the observed proportions in the study MW2004-11-02, the number of subjects to be enrolled to achieve a power of 90% for the non-inferiority test is $n = \frac{2D}{p_1 + p_2} = 2164$ (1082 in each group).

Estimate based on study MW2010-03-02

Estimated log hazard ratio from study MW2010-03-02 (NexoBrid versus SoC) = 1.56, using a Cox proportional hazards model with shared frailty adjusted for center, age, %TBSA, proportion of the FT area of a patient and number of TWs (1,2,3-4, ≥5).

Standard error = 0.41

Target log hazard ratio = 1.56 - 0.41/2 = 1.36; target hazard ratio $\lambda = 3.90$.

The formula for total number of events D is: $D = \frac{4(z_{\alpha} + z_{\beta})^2}{(\ln \lambda)^2}$

(Piantadosi, Clinical Trials: A Methodologic Perspective, p.169)

 $z_{\alpha} = 1.96$;

 z_{β} = 1.28 for 90% power.

If the proportion of events in NexoBrid group is denoted by $p_1 = 0.62$

and the proportion of events in SoC group is denoted by $p_2 = 0.73$,

which are the observed proportions in the study MW2010-03-02, the number of subjects to be enrolled to achieve a power of 90% for the non-inferiority test is $n = \frac{2D}{p_1 + p_2} = 34$ (17 in each group).

Cosmesis and Function: MVSS at 12 months

Estimate based on study MW2004-11-02

Estimated difference in MVSS at 24 months from previous study (NexoBrid vs. SoC) = 3.32 - 3.83 = -0.51.

Standard error = 0.50

Target difference $\Delta = -0.51 + 0.50/2 = -0.26$.

The formula for the number of patients per group n is: $n = \frac{2(z_{\alpha} + z_{\beta})^2 \sigma^2}{q(\Delta - d_0)^2}$

where

 $z_{\alpha} = 1.96$;

 z_{β} = 1.28 for a power of 0.9;

 σ = the estimated common standard deviation= 2.33 (taken from previous study);

 d_0 = clinical equivalence level = 1.9;

q = proportion who are retained in follow-up to 12 months = 0.7 (assuming 30% loss to follow-up over 1 year)

For 90% overall power, the required sample size per group is 35 (70 overall).

Estimate based on study MW2010-03-02

Estimated mean MVSS at 12 months from study MW2010-03-02: NexoBrid 3.70; SoC 5.08

Standard errors: NexoBrid 0.24; SoC 0.38

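### The wound-level closure and eschar-removal models take size and depth only from whole-patient values, although each target wound's own size and depth are recorded; adding them is a cheap, modest gain in precision

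*SAP*

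**What the plan says.** SAP 11.1.5.1 compares wound closure between arms at wound level, with a 7-day margin: "This will be done by adding 7 days to the wound closure times in the SoC group". The covariates are center, age, %TBSA, FT share and number of target wounds (TWs). The list gives no level for %TBSA; the definitions under the SAS code do: "tbsa is the overall percent TBSA of a patient, pctFT is the proportion of the FT area of a patient". The accelerated failure time (AFT) fallback uses indicators for the patient's %TBSA and FT strata. In 11.1.3, the additional wound-level analysis of eschar removal has the same definition: "TBSA is the overall percent TBSA of a patient".

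Elsewhere the level differs:
- The GEE model for autograft incidence (11.1.4.4) lists "TBSA (wound level), proportion of the FT area of a patient", so size is per wound and depth per patient.
- In 13.3, the MW2004-11-02 closure estimate was "adjusted for center, age, %TBSA area of the wound and number of TWs".
- The MW2010-03-02 closure estimate in 13.3 lists %TBSA without a level, plus patient FT share.

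Section 7.2.1 records SPT, DPT and FT %TBSA separately for each target wound at screening.

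**The concern.** Two wounds of one child, say a small deep-partial and a large full-thickness one, receive identical covariates. The SAP's own background (2.1) expects them to close by different routes, with grafting kept for full-thickness wounds and epithelialization where dermis survives. A shared frailty or a patient-clustered variance deals with correlation within a child; neither explains why one wound closes later than another. The supportive covariates in 11.1.1 (gender, SPT share over all TWs, time from injury, number of TWs) are not wound-specific either.

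Leaving a prognostic covariate out of a Cox model pulls the treatment coefficient towards zero. Here non-inferiority is shown by NexoBrid being ahead after the 7-day shift, so attenuation works against showing it. There is also a consistency question: one of the two sizing estimates for this endpoint comes from a model with the wound's own area, which the planned model lacks.

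**Working it through.** **1. Inputs.** Two-sided 5% ("all statistical tests will be conducted against a two-sided alternative hypothesis, employing a significance level of 0.05", 11.1.9), so z = 1.96; "1.28 for 90% power" (13.3). On the MW2004-11-02 basis, "Target log hazard ratio = 0.49 - 0.63/2 = 0.18" with event proportions 0.64 and 0.56. On the MW2010-03-02 basis, target log HR 1.36 with 0.62 and 0.73. Allocation is 1:1 and 145 patients were enrolled.

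**2. The plan's figures.** D = 4(1.96 + 1.28)² / (log HR)² and n = 2D / (p1 + p2).
- MW2004-11-02: D = 41.99 / 0.0324 = 1296, n = 2592 / 1.20 = 2160. With unrounded z values D rounds up to 1298, n = 2163.3, hence the SAP's 2164.
- MW2010-03-02: D = 41.99 / 1.8496 = 22.7, n = 45.4 / 1.35 = 33.6, hence 34.

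Both reproduce. (0.49 − 0.63/2 is 0.175; without rounding to 0.18, n would be about 2286.)

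**3. Power with 145 patients by the same formula.** Power = Φ(|log HR|·√D / 2 − 1.96).
- MW2004-11-02: D = 145 × 0.60 = 87; 0.18 × 9.33 / 2 = 0.84; Φ(−1.12) = 13.1%.
- MW2010-03-02: D = 145 × 0.675 ≈ 98; 1.36 × 9.89 / 2 = 6.73; power above 99.99%.

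If omitted covariates shrank the log HR by 10%, these become 11.4% and above 99.99%; by 20%, 9.9% and 99.97%.

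**4. Simulation.** The documents give neither the prognostic effect of wound size or depth nor the distribution of TWs per patient, so both are assumed. Marginal Cox models with patient-clustered variance were fitted to 800 trials per cell of 145 patients, with patient frailty SD 0.5 and about 60–70% events. The treatment effect was set on the already shifted scale. The first model had patient total area, patient FT share and number of TWs; the second added the wound's log size and FT share. Center and age were left out of both. Power (%), patient-level terms only → wound terms added:

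| log HR | Prognostic log HR per SD | 75% of patients with one TW | 45% of patients with one TW |
|---|---|---|---|
| 0.18 | 0 | 13.4 → 13.6 | 18.0 → 18.1 |
| 0.18 | 0.25 | 13.1 → 14.1 | 15.4 → 15.8 |
| 0.18 | 0.5 | 14.9 → 17.0 | 16.4 → 17.2 |
| 0.18 | 0.8 | 13.4 → 15.6 | 13.6 → 18.0 |
| 0.5 | 0 | 66.1 → 66.2 | 77.0 → 77.2 |
| 0.5 | 0.25 | 65.6 → 66.7 | 78.1 → 80.2 |
| 0.5 | 0.5 | 64.2 → 67.9 | 71.8 → 76.7 |
| 0.5 | 0.8 | 56.8 → 67.5 | 65.9 → 76.7 |
| 1.36 | any | 100 → 100 | 100 → 100 |

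The gain comes from less attenuation, not a smaller standard error. In the 0.5 / 0.8 cell with 45% single-TW patients, the median coefficient rises from 0.375 to 0.466 and its standard error from 0.154 to 0.167.

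**5. Type I error.** At zero effect, one-sided rejection (nominal 2.5%) was 2.0–4.4% with patient terms only and 2.2–4.5% with wound terms. The largest gap was 2.0% against 4.1%, the larger model being higher. The omission therefore shows no inflation.

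**6. Equal closure in both arms.** A smaller simulation (250 trials per setting, about two wounds per patient) applied the 7-day shift to equal closure. Power rose from 50.8% to 53.2% with a moderate depth effect (FT log HR −1.0), from 44.0% to 51.6% with a strong one (−1.5), and from 50.0% to 52.0% in a third setting. The Monte Carlo standard error of each figure is about √(0.25/250) = 3.2 points, so only the strong-effect gain is clearly larger than that.

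**The case against.** Center, age, %TBSA and patient FT share are the minimization factors (11.1.11, 13.1), and treatment is allocated by patient, so adjusting for them is coherent. The same set serves the primary endpoint, surgical excision and MVSS. The newer MW2010-03-02 estimate used patient FT share, and no model of closure or autograft in the SAP has a wound-level FT term. Where a child has one TW, patient and wound values largely coincide, though not entirely: the stratum in 11.1.11 is defined on the total burned area, which may include burns outside the TWs. All of this stands, and it makes the current covariate set defensible.

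Two stronger readings are tempting. A reader might infer that the omission materially costs power in the main non-inferiority safety test. The documents do not support that. At the SAP's own planning effects the gain is 0–4 points on a low base, or nil. Larger gains need an intermediate effect that 13.3 does not state and prognostic effects that the documents do not give. Closure lies outside the testing hierarchy in 11.1.9, and MVSS at 12 and 24 months is also tested against a margin. Wound-level eschar removal is only an additional analysis, so no main efficacy test is touched.

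A reader might also infer that imbalance in depth between arms goes uncorrected. Between patients it is largely handled by minimization and the patient-level covariates; what remains is the wound-to-wound part within a child.

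Finally, only the marginal Cox branch was simulated. The size of any gain under the frailty or AFT branch is not established.

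**Conclusion.** The mismatch is real: a wound-level analysis with whole-patient size and depth terms, in a SAP that collects wound-level values and uses wound-level size elsewhere. It is not a validity error. The benefit of correcting it is a modest, assumption-dependent improvement in precision, in the sense of the estimate relative to its standard error: about 0–4 points of power at log HR 0.18, nil at 1.36, and roughly 1–11 points at 0.5 if wound size and depth are prognostic. Those ranges rest on the assumed prognostic effects, wound counts and frailty, and on the marginal Cox model. The change is worth making because it is nearly free and matches the covariates to the unit of analysis, not because the planned test is unsound.

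**What to change.** In the wound-level Cox, frailty and AFT closure models of 11.1.5.1, prespecify the wound's own %TBSA on the log scale and its FT fraction, both from the screening assessment, as added covariates. Do the same in the additional wound-level eschar-removal analysis of 11.1.3. Keep the patient-level terms and the clustered variance or frailty. State the level of %TBSA in the covariate list of 11.1.5.1, and reconcile it with 11.1.4.4 and the MW2004-11-02 estimate in 13.3.

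The cost is two covariates already in the database. The hazard ratio becomes conditional on wound size and depth and should be labelled so. Two more terms also enter the all-covariate proportional-hazards test at the 10% level, which decides the model used, so the change must be fixed before the data are analyzed.
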